1. Measure the levels of HMGB-1 in patients with acute stroke. We currently have the tools available to measure the levels of HMGB-1 in humans by ELISA (IBL-International, Toronto; ST51011).

2. Measure the level of cytokines, DAMPs and growth factors downstream from HMGB-1 secretion. If we find that levels of HMGB-1 are elevated after stroke, we will assay the levels longitudinally over a 3 month period. We will return to the bio-repository to assay samples for IL-1, IL-6, IL-8, IL-10, TNF and BDNF, all molecules known to be stimulated by HMGB-1 secretion [4, 5], and for which there are well developed ELISA protocols and further there are well developed assays for the Meso-Scale Diagnostics (MSD: Gaithersberg,MD) in the [name] lab. The interleukins and TNF are well known cytokines involved in pro-inflammatory response. BDNF is a growth factor involved in repair [6, 7]. As HMGB-1 levels are negligible in normal healthy volunteers we do not expect that patients with acute stroke will have low levels. While there is some support to use a published lower level of 20 ng/ml as a cutoff for further cytokine and growth factor analysis [5], it seems prudent under the circumstances of the current lack of knowledge about the longitudinal characterization of cytokines and growth factors after stroke to

analyze the blood samples over time for HMGB-1 and for the cytokines and growth factors mentioned.

3. Compare the level of cytokines individuals with acute stroke with those of age-matched, healthy controls. In order to establish baseline cytokine levels, we will collect serum samples from healthy, age-matched controls and assay them for HMGB-1, IL-1, IL-6, IL-8, IL-10, TNF, and BDNF. We predict that cytokine levels will be negligible in healthy subjects and their samples will serve as a control for individuals post-stroke.

Background and Significance

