Ischemia and reperfusion triggers innate immune response first in the compromised vessel, in the perivascular and the brain parenchymal space. Early innate immune events follow clotting, platelet-leucocyte aggregation, complement activation [15, 16], increased arachidonic acid metabolites and reactive oxygen species [17, 18], and cytokine release, especially IL-1 [19-21]. Up-regulation and release of selectins, integrins [22, 23], proteases (like matrix metalloproteinases) [24, 25], and loss of NO (nitric oxide) [26] provide platforms for leucocyte adhesion, rupture of the blood-brain barrier, and matrix proteolysis. Mast cell degranulation releases histamine and additional proteases increasing signals for inflammatory cell migration to blocked and leaky vessels. The parenchyma of the brain fares no better; cytokines and chemokines [27-30] disrupt the microglia-neuron communication and TNF, depending on its source [31-34], provokes continued pro- but also insufficient anti-inflammatory signals and ATP is released, extracellular glutamate rises and cells die. Left out of this brief highlight summary of the early response of the immune system to stroke is the complete list of activated and secreted cytokines; including IL-6, IL-10, IL-12, IL-17, IL-18, IL-20, IL-23 [35-41], growth factors [42-44], and enzymes [26, 45, 46]. Persistent cell death initiates a new phase of the immune physiology the adaptive response. Altering these complex cascades will be a challenge. Furthermore, any intervention will require a certain immediacy and timeliness that currently exceeds standard and even premium health care delivery systems. More likely effective interventions will come from elucidation of the ongoing inflammatory response.

Interferon and TGF sensitize and prime T cells and antigen presenting cells (dendritic cells), and danger associated pattern molecules (DAMP) like HMGB-1 which in turn activate toll like receptors (TLR). Recent work on the humoral immune response has focused on the increased

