We know that overwhelming sepsis and stroke are different conditions and impose a number of different stresses on the patient/experimental animal. However, the two conditions share some molecular mediators; especially HMGB-1. Also both stroke and sepsis cause immediate rise in TNF and IL-1, sentinels in the innate immune system. High levels of these cytokines persist for hours to days in mice, but return to baseline by 3 days. This first wave of cytokines is followed by a later but more sustained elevation of HMGB1. Increased levels of HMGB1 persist for weeks with a return to baseline levels in mice at around eight weeks following the initial insult. This information is not entirely clear in animal stroke models or in patients with stroke, a void that this protocol intends to correct.

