We will obtain blood samples from 100 consecutive patients with ischemic or hemorrhagic stroke admitted to the Northwell stroke service. As we are interested in assay of HMGB-1 from the time from stroke, the admission sample timing with respect to stroke will be noted and we will obtain subsequent blood samples at 7, 14, 30 and 90 days after the time that the stroke occurred. So if the patient comes in 24- or 48-hours after the onset of symptoms, we will collect the admission sample and collect the 7-day sample 6 or 5 days after admission respectively. Given the challenges of collecting samples within a 24 hour time period, the collection window will be extended such that day 7 and day 14 samples will be collected plus or minus one day of the target (e.g. between day 6-8 or day 13-15, respectively) and day 30 and day 90 samples will be collected plus or minus 7 days of the target (e.g. between day 23-37 and day 83-97, respectively). Each of the 5 samples will be 4 cc each (green top tube). We will also obtain a one-time DNA sample, via the collection of a 10cc lavender tube (EDTA) at the time of the first sample collection. If this is not possible we will collect this sample at the time of a subsequent research blood sample collection. The total volume of blood drawn for each study subject will be no more than 30 cc over the duration of the study. Additionally, we will collect a one-time blood sample from up to 30 healthy, age-matched controls. Control subjects will be NSLIJHS employees, members of the local community recruited with the Northshore Recruitment Registry and GAP Registry recruitment tools, and enrolled subjects' family members recruited by the Research Coordinator and Principal Investigator. Each control sample will be 4cc total (green top tube)

The blood will be centrifuged and prepared for HMGB-1 analysis by NS-LIJ Biorepository staff. If we miss sample collection across the 7, 14, 30, and 90 day time points the available collected samples from a subject will be analyzed. We will measure HMGB-1 and if the levels are elevated (>20ng/ml) we will return to the banked samples in the bio-repository to repository to assay samples for IL-1, IL-6, IL-8, IL-10, TNF and BDNF, all molecules known to be stimulated by HMGB-1 secretion [4, 5].

The following data will be collected for each subject with stroke:

- Age (at time of stroke)
- Gender
- Stroke risk factors (history of hypertension, smoking, estrogen supplements)

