The Tissue Donation Program (TDP) collects and stores biological samples and associated clinical data as a resource for investigators in the Northwell Health System. Through the development and implementation of tissue specific sub-protocols, these materials may be available to the larger biomedical community. A portion of each blood sample collected for this study will be stored by the TDP and made available for future research according to TDP established procedures.

Plasma will be stored from each blood sample collected. DNA will be isolated and stored once on each patient with stroke at the time of the first blood collection. If for some reason this is not possible, a DNA sample will be isolated from the next available blood sample.

These samples stored by the TDP can be shared by other investigators who submit protocol for use of stored samples to the TDP's Committee for Participant Protection (COPP). Once approved by the COPP, stored samples and associated clinical data can be distributed to the investigator in a completely de-identified fashion. Investigators receiving samples will not have access to the link between a bar coded label and subject identity.

Statistical Considerations and Data Analysis

Specific Aims:

1. Measure the levels of HMGB-1 in patients with stroke. Because the level of HMGB-1 in healthy control subjects is negligible and because survivors of sepsis had levels of HMGB-1 < 20 ng/ml, we believe it is reasonable to assume that levels above 20ng/ml are not normal [5]. Also we are collecting longitudinal samples and we expect that if the pro-inflammatory condition clears in these patients with stroke the HMGB-1 level will fall below 20 ng/ml if not lower.

2. Measure the level of downstream pro-inflammatory molecules and growth factor. We will measure IL-1, IL-6, IL-8, IL-10, TNF and BDNF, all molecules known to be stimulated by HMGB-1 secretion. If we find that HMGB-1 is elevated we expect to find elevations in the other

molecules. If HMGB-1 is not elevated it will be important to measure the serum level of the other cytokines to insure that some other pathophysiology of stroke and stroke recovery is not also involved in activating cytokines. The serum growth factor BDNF level may change in an alternate direction.

Endpoint Variables:

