1. HMGB-1
2. Downstream cytokines activated by HMGB-1 including: TNF;IL-1; IL-6; IL-8; IL-10; and growth factor, BDNF.

3. Compare the level of cytokines individuals with acute stroke with those of age-matched, healthy controls. In order to establish baseline cytokine levels, we will collect serum samples from healthy, age-matched controls and assay them for HMGB-1, IL-1, IL-6, IL-8< IL-10, TNF, and BDNF. We predict that cytokine levels will be negligible in healthy subjects and their samples will serve as a control for individuals post-stroke.

Statistical Methods.

This will be a prospective pilot study of patients diagnosed with acute stroke. We will obtain serial blood samples (admission, 7, 14, 30, 90 d after stroke) to examine whether the blood levels of HMGB-1, and TNF,IL-1, IL-6, IL-8, IL-10, and BDNF are elevated, and if they are, determine their temporal characteristics.

Recruitment of patients with stroke will take place among those who admitted to North-Shore and LIJ hospital stroke service.

Specific Statistical Aims. In this pilot we will gather information from patients in the acute phase of stroke and the early recovery phase of stroke. We aim to measure over a three month period the HMGB-1 level, and the downstream pro-inflammatory cytokines such as TNF, IL-1, IL-6, IL-8 and IL-10, and also the growth factor BDNF. We plan to evaluate these serum levels in 100 patients. This data will permit a formal estimate of the number of patients required to determine correlation among the cytokines and growth factor levels, and also correlation with stroke severity and possible disability outcome.

Outcome Variables. The following variables will be collected from the study group. Blood will be collected on admission, 7 14, 30 and 90 days after stroke. We will also collect stroke type – ischemic or hemorrhagic; stroke severity as measured by the NIH stroke scale; stroke outcome as measured by the Ranking scale.

Statistical Analysis. The statistical analysis for this pilot study will be primarily descriptive in nature. The main statistical analysis will employ repeated measures analysis to describe the patterns of change in HMGB-1 and the cytokine values over time. Other techniques will be explored if the data warrant it; such as examining pairs of outcome variables (HMGB-1 and TNF, HMGB-1 and IL-1, or HMGB-1 and stroke severity; as pioneered at Feinstein by Dr. [name] and as in [57]).

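### Raised cytokines alongside raised HMGB-1 cannot separate an HMGB-1 effect from a parallel response to stroke, yet endpoint 2 is labelled causally and another cause is sought only when HMGB-1 is not elevated

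*Combined protocol and SAP*

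**What the plan says.** In Statistical Considerations and Data Analysis, Specific Aim 2 has two branches.

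- **HMGB-1 elevated:** "If we find that HMGB-1 is elevated we expect to find elevations in the other" molecules. No other explanation is examined here.
- **HMGB-1 not elevated:** "If HMGB-1 is not elevated it will be important to measure the serum level of the other cytokines to insure that some other pathophysiology" is not also activating them.

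Under Endpoint Variables, endpoint 2 is titled "Downstream cytokines activated by HMGB-1 including" TNF, four interleukins and BDNF, with no condition attached.

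The background gives a rival explanation. Background and Significance lists other early triggers around cytokine release: "Early innate immune events follow clotting, platelet-leucocyte aggregation, complement activation" and more. Progress Report/Preliminary Studies adds: "Also both stroke and sepsis cause immediate rise in TNF and IL-1, sentinels in the innate immune system". It continues: "This first wave of cytokines is followed by a later but more sustained elevation of HMGB1".

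The Statistical Analysis paragraph is descriptive, with repeated-measures analysis of change over time. Pairs such as HMGB-1 and TNF are examined only if the data warrant it, citing a within-subject correlation method (reference 57). Severity stratification is only a potential secondary analysis. NIH Stroke Scale and concurrent infection at the time of stroke are recorded, but neither is assigned a role as a covariate.

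**The concern.** In the branch the plan expects for acute patients, a raised cytokine fits the stated expectation whether HMGB-1 drove it or the stroke raised both markers separately. Nothing in that branch could count against HMGB-1, and the endpoint's name already supplies the causal reading. The check for another mechanism sits in the branch the plan does not expect in the acute phase; Specific Aims, Aim 2 says "we do not expect that patients with acute stroke will have low levels".

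What is at stake is how the pilot is read. Its data are meant to size later work on correlation among these markers and with severity and possibly disability. A finding that stroke raises several markers could be carried forward as evidence that HMGB-1 activates the rest.

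**Working it through.** The plan gives no figure to reproduce: 100 patients and 30 controls is a convenience sample, with no effect size or SD. The check is whether the expected pattern appears when HMGB-1 has no effect at all.

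**Set-up.** From the plan: 100 patients sampled at admission and days 7, 14, 30 and 90; 30 controls sampled once. Assumed:

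- both markers on a log scale with residual SD 1, and admission taken as day 1;
- the same initial stroke-driven shift in both markers;
- HMGB-1 decaying with a time constant of 60 days, and the cytokine with 3, 14 or 60 days;
- zero effect of HMGB-1 on the cytokine.

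*Elevated* means patients above controls at z > 1.96. There were 300 simulated studies per row.

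**Hand check of one cell.** SE = √(1/100 + 1/30) = 0.208. Take a shift of 1 SD and cytokine decay of 3 days.

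- HMGB-1 at day 1: exp(−1/60) = 0.983; z = 0.983/0.208 = 4.72; chance of elevation Φ(4.72 − 1.96) = 0.997.
- Cytokine at day 1: exp(−1/3) = 0.717; z = 3.44; Φ(3.44 − 1.96) = 0.931.
- Joint: 0.997 × 0.931 = 0.93, against 0.91 simulated.

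**No shared patient factor, no HMGB-1 effect** (per cent of studies; the last column is the within-subject correlation not adjusted for visit, nominal level 5%):

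| Shift (SD) | Cytokine decay (days) | Joint, admission | Joint, day 7 | Joint, day 30 | Joint, day 90 | Within-subject correlation significant |
|---|---|---|---|---|---|---|
| 0.5 | 3 | 27 | 3 | 1 | 0 | 4 |
| 0.5 | 14 | 40 | 15 | 0 | 0 | 9 |
| 0.5 | 60 | 42 | 33 | 11 | 1 | 5 |
| 1 | 3 | 91 | 5 | 2 | 0 | 18 |
| 1 | 14 | 100 | 81 | 8 | 0 | 43 |
| 1 | 60 | 100 | 99 | 68 | 3 | 41 |
| 1.5 | 3 | 100 | 12 | 1 | 0 | 57 |
| 1.5 | 14 | 100 | 99 | 15 | 1 | 95 |
| 1.5 | 60 | 100 | 100 | 99 | 10 | 93 |

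Here the two markers are linked only by time. The within-subject correlation still reaches significance in 18–95% of studies at shifts of 1 SD or more, because both fall. Removing the visit means brings it to about 0.

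**Adding a shared patient factor** such as severity or infection, still with no HMGB-1 effect. The admission correlation becomes 0.14–0.19 for a moderate factor (loading 0.5 on both markers) and 0.41–0.49 for a strong one (loading 1). It returns to about 0 once that factor is adjusted for. The visit-adjusted within-subject correlation is then 0.01–0.02 (moderate) or 0.05–0.09 (strong). Adjustment for visit therefore removes most, but not all, of the spurious association.

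**The case against.** The strongest reply is that this is a descriptive pilot. Its stated purpose is to find out whether HMGB-1 is elevated, and Aim 2 voices an expectation, not a decision rule. That stands. A reader might infer that the pilot will report joint elevation as support for an HMGB-1-driven cascade in almost any cohort. The documents do not say so, and the test applied above is mine.

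Four further points are fair.

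- **Joint elevation is not assured at every visit.** Sample Size Justification says some cytokines are gone within hours to days, and the table shows how quickly joint elevation can fade.
- **The low-HMGB-1 branch is not empty throughout.** The expectation of few low values concerns acute stroke. Aim 1 of the statistical section anticipates levels below 20 ng/ml as the condition clears, so later visits may supply low samples.
- **The time order is not settled for patients.** The 3-day and eight-week timings are from mice, and the same section says the picture in stroke is unclear. Preliminary data show raised HMGB-1 in some patients hours after onset. It goes too far to say the early cytokines cannot be downstream.
- **The plan is not silent on the relation.** It allows HMGB-1/cytokine pairs and compares cytokines with controls without conditioning on HMGB-1. The pair analysis, however, is optional, and no adjustment for visit, severity or infection is stated.

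The label may also rest on prior literature, since the plan describes these molecules as known to be stimulated by HMGB-1. That explains the wording, but does not make joint elevation in this cohort informative about cause.

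**Conclusion.** The point holds in limited form. Joint elevation, most likely at admission and less so later, cannot distinguish an HMGB-1 effect from a parallel response to stroke. The unconditional label and the one-sided search for another cause invite the wrong reading. With no HMGB-1 effect, joint elevation at admission appeared in 91–100% of simulated studies at an assumed shift of 1 SD and 21–42% at 0.5 SD, across all three decay times and with or without a shared factor. At day 7 with 3-day decay it was 2–12% across all shifts. These sizes rest on assumed shifts, decay times and loadings; the logical point does not. The optional pair analysis would not resolve the matter unless adjusted for visit.

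The documents do not support the stronger claim that the study is set to declare causation, or that joint elevation will appear whatever happens.

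**What to change.** 1. **Label.** Retitle endpoint 2 *other cytokines and BDNF*, and state that joint elevation is not evidence that HMGB-1 activated them.
2. **Planned association analysis.** Make the pair analysis planned instead of optional: a repeated-measures model of each log cytokine on same-visit log HMGB-1 in all stroke patients. Covariates are visit (or time since stroke), NIH Stroke Scale and recorded concurrent infection. Report within-patient and between-patient slopes with intervals, as association only. In simulation, a same-visit association adjusted for visit and severity gave about 5% false positives when severity and time were the only shared causes.
3. **Comparison with controls and assay rule.** Report the stroke-versus-control cytokine difference at each visit whatever the HMGB-1 level. Research Design and Methods says "if the levels are elevated (>20ng/ml) we will return to the banked samples" for the cytokine assays. Specific Aims, Aim 2 favours analysing the samples over time regardless, and the statistical section wants cytokines measured when HMGB-1 is not elevated. Reconcile these so that low-HMGB-1 samples are also assayed; otherwise the one stated check for another mechanism is lost.

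Two tempting additions should be avoided. A regression on the preceding visit's HMGB-1 is not a sound test of *downstream*: gaps between scheduled visits reach 60 days. In simulation it detected a true same-visit slope of 0.3 in about 7% of trials and fired falsely in 37–92% with an unmeasured shared factor. A stroke-control contrast at a fixed HMGB-1 level may be extrapolation at admission, where patient and control values may barely overlap.

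The cost is wording, modest extra analysis, a more cautious claim and possibly some added assays, depending on how the assay rule is reconciled. Infection is recorded only at the time of stroke, and unmeasured shared causes remain, so the data can show association but not causation.

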1. HMGB-1
2. Downstream cytokines activated by HMGB-1 including: TNF;IL-1; IL-6; IL-8; IL-10; and growth factor, BDNF.

3. Compare the level of cytokines individuals with acute stroke with those of age-matched, healthy controls. In order to establish baseline cytokine levels, we will collect serum samples from healthy, age-matched controls and assay them for HMGB-1, IL-1, IL-6, IL-8< IL-10, TNF, and BDNF. We predict that cytokine levels will be negligible in healthy subjects and their samples will serve as a control for individuals post-stroke.

Statistical Methods.

This will be a prospective pilot study of patients diagnosed with acute stroke. We will obtain serial blood samples (admission, 7, 14, 30, 90 d after stroke) to examine whether the blood levels of HMGB-1, and TNF,IL-1, IL-6, IL-8, IL-10, and BDNF are elevated, and if they are, determine their temporal characteristics.

Recruitment of patients with stroke will take place among those who admitted to North-Shore and LIJ hospital stroke service.

Specific Statistical Aims. In this pilot we will gather information from patients in the acute phase of stroke and the early recovery phase of stroke. We aim to measure over a three month period the HMGB-1 level, and the downstream pro-inflammatory cytokines such as TNF, IL-1, IL-6, IL-8 and IL-10, and also the growth factor BDNF. We plan to evaluate these serum levels in 100 patients. This data will permit a formal estimate of the number of patients required to determine correlation among the cytokines and growth factor levels, and also correlation with stroke severity and possible disability outcome.

Outcome Variables. The following variables will be collected from the study group. Blood will be collected on admission, 7 14, 30 and 90 days after stroke. We will also collect stroke type – ischemic or hemorrhagic; stroke severity as measured by the NIH stroke scale; stroke outcome as measured by the Ranking scale.

Statistical Analysis. The statistical analysis for this pilot study will be primarily descriptive in nature. The main statistical analysis will employ repeated measures analysis to describe the patterns of change in HMGB-1 and the cytokine values over time. Other techniques will be explored if the data warrant it; such as examining pairs of outcome variables (HMGB-1 and TNF, HMGB-1 and IL-1, or HMGB-1 and stroke severity; as pioneered at Feinstein by Dr. [name] and as in [57]).

Potential secondary analysis includes stratification by stroke severity.

SAMPLE SIZE CONSIDERATIONS

The proposed sample size is 100 consecutive patients with stroke and 30 healthy, age-matched controls. This sample size is a sample size of convenience based on feasibility and availability of resources and is not based on any formal power calculations.

Sample Size Justification

This is a pilot study, the purpose of which is to determine if HMGB-1 is elevated in patients after stroke. There is scant longitudinal clinical information about HMGB-1 in patients with stroke, and the current information about some of the other cytokines is that they are gone within hours- days. Recent hospital data from the stroke service indicate admission of 600 patients with stroke per year at Northwell and 300 per year at LIJ. The rehabilitation service admits around 700 patients with stroke per year. We should be able to gain complete information (admission, 7, 14, 30 and 90 days after stroke) on 100 patients within two years.

Protection of Human Subjects

RISKS TO SUBJECTS:

Human Subjects Involvement & Characteristics: We anticipate enrolling 100 human. Inclusion and exclusion criteria are stated above in the Research Design and Methods section.

Sources of Materials: Sources of research material on patients with stroke will be obtained specifically for this study from existing health records and we will obtain blood specimens.

Potential Risk: Minimal risks of blood withdrawal include pain from the needle being inserted through the skin into the vein, bruising, clot formation under the skin, lightheadedness, possible fainting and rarely infection.

One additional risk concerns the risk to confidentiality incurred with any collection of medical data.

ADEQUACY OF PROTECTION AGAINST RISKS:

Recruitment and Informed Consent: Patients with acute stroke will be initially identified either by clinicians in the Northshore-LIJ Health System or by the Research Informatics Department at Feinstein who will extract candidacy information through Sunrise Clinical Manager Software. [name], Chair of Neurology is aware of these studies and we will require the active participation of the Stroke team led by [name] and the participation of his colleague [name]. Also, [name], Chair of Physical Medicine and Rehabilitation is aware of these studies and will direct us to the participating residents. Additional Northwell Health System physicians who have appropriate patient populations will be made aware of the research study protocol and procedures, and given an overview of the study through contacts with the study personnel. [name], Director of Research Informatics at the Feinstein Institute of Medical Research is also aware of these studies and will develop software with his team to extract candidacy information from Sunrise Clinical Manager, including patient name/age, stroke type/location, admission date/admission status, medical record number, and contact information. This information will be provided to the study coordinator to identify potential study participants efficiently within the acute time window. The study coordinator will then contact treating physicians with the names of potential patients before contacting the patients for

recruitment. The patient will then be contacted by either the study coordinator (with permission of the treating physician) or the treating physician directly. If the patient expresses interest in participation, consenting study personnel or the physician will obtain informed consent (if the physician is listed as an investigator on this study). Alternatively, the physician may either, 1) provide the patient with the study coordinator's contact information or 2) provide the patient's contact information to study personnel with the patient's permission, which will be documented in the medical record.

If the patient is unable to provide consent and a family member is not present, the study coordinator (with permission of the treating physician) will phone the patient's next-of-kin in the following order of contact: patient's spouse, patient's child, patient's parent, patient's extended family (e.g. aunt/uncle, niece/nephew). During the phone call, the coordinator will discuss the study and arrange a time to meet and sign the consent form if the family member voices interest in the patient's participation.

After a discussion about the study with a potential subject or a potential subject's legally authorized representative (LAR), interested parties will be given a copy of the consent form by one of the study investigators. The investigator will review and explain the consent form. All information about the study will be provided. Ample time will be given for individuals to ask questions regarding participation and to have questions answered prior to signing the consent form. If so desired, those interested will be given a copy of the consent form so that they may have the opportunity to discuss participation further with family and/or advisors. Only those investigators listed in the study protocol will obtain informed consent. If an individual chooses to enroll, the consent form will be signed before participation begins. Once an individual joins the study and informed consent is obtained, the subject will receive a signed copy of the consent form. The subject may withdraw from the study at any time without repercussions to subsequent care.

If the patient is awake, alert, and oriented to person, place, and time, and demonstrates appropriate cognitive and communicative abilities as determined by the treating physician, the patient will be deemed to have the appropriate capacity to consent.

If it is determined that a patient is unable to consent for him/herself, due to a lack of capacity or lack of comprehension, consent will be sought from the patient's LAR. Assent from the adult patient will be obtained as appropriate. If such a subject regains his/her ability to make healthcare decisions, he/she will be given the opportunity to provide consent. This consent will be documented using the Addendum to Consent by Research Proxy for Continuing Participation in a Research Study form.

If the patient provides the consent delegate with assent to participate in the research but, due to a physical disability, is unable to sign the consent form, two witnesses will sign the document affirming their presence during the consent process and the patient's physical disability as reason for an absent signature.

Healthy, age-matched control subjects will be recruited from NSLIJHS employees, enrolled subjects' family members, and members of the local community identified by the Northshore Recruitment Registry and GAP Registry recruitment tools. Recruitment will be done with direct contact or via telephone and will not be done by anyone who has, or can anticipate having, a supervisory role over the employee.

A study investigator will obtain informed consent from interested persons. After a discussion about the study with a potential subject, interested persons will be given a copy of the consent form by one of the study investigators. The investigator will review and explain the consent form to the person. All information about the study will be provided. Ample time will be given for persons to ask questions regarding participation and to have questions answered prior to signing the consent form. If so desired, those interested will be given a copy of the consent form so that they may have the opportunity to discuss participation further with family and/or advisors. Only those investigators listed in the study protocol will obtain informed consent. If a person chooses to enroll, the consent form will be signed before participation begins. Once an individual joins the study and informed consent is obtained, the subject will receive a signed copy of the consent form. The subject may withdraw from the study at any time without repercussions to subsequent care.

Protection Against Risk: Experienced and certified personnel, using standard precautions to avoid unnecessary complications related to the procedure, will perform phlebotomy. Whenever possible, blood draw will occur concurrently with blood draws being performed for routine patient care.

To protect subjects' confidentiality, each subject will be assigned a number, and all samples and data will be stored with the subject number only and not the subject's name. Data will be stored on a password-protected computer. Subject charts with medical history and assigned subject numbers will be kept in locked file cabinets in the CRC. Access to charts will be granted only to study investigators and CRC staff. Charts will be kept confidential and will not be shared with any third parties without permission from the subject.

POTENTIAL BENEFIT TO THE SUBJECTS AND OTHERS:

The subjects enrolled in this study will not benefit directly due to their participation. However, the information obtained from this study may benefit patients suffering from spinal cord injury, in the future. The risks to subjects are reasonable in relation to the anticipated benefits to others.

SCIENTIFIC VALUE:

The results of this study may help to improve stroke recovery.

Inclusion of Women and Minorities

Subjects will be selected without regard to gender, race, or ethnicity. Recruitment flyers will be posted around the Northwell Health System, as many uninjured adults visit or accompany friends and family members to the outpatient and inpatient facilities. Given the size and location of the health system, we believe that we will reach a multiethnic/multiracial audience of both genders. If we find that members of minority groups are not responding to the flyers, we will post additional flyers in neighborhoods with larger proportions of those minorities.

Inclusion of Children

Children will be excluded from this study because the incidence of such patients is low enough at NSLIJ that we cannot expect to recruit them.

REFERENCES

1. Andersson, U. and K.J. [name], *HMGB1 is a therapeutic target for sterile inflammation and infection*. *Annu Rev Immunol*, 2011. 29: p. 139-62.
2. Wagner, T.H., et al., *An economic analysis of robot-assisted therapy for long-term upper-limb impairment after stroke*. *Stroke*, 2011. 42(9): p. 2630-2.
3. Lo, A.C., et al., *Robot-assisted therapy for long-term upper-limb impairment after stroke*. *N Engl J Med*, 2010. 362(19): p. 1772-83.
4. Andersson, U., et al., *High mobility group 1 protein (HMG-1) stimulates proinflammatory cytokine synthesis in human monocytes*. *J Exp Med*, 2000. 192(4): p. 565-70.
5. Wang, H., et al., *HMG-1 as a late mediator of endotoxin lethality in mice*. *Science*, 1999. 285(5425): p. 248-51.
